### **d) Study Procedures and Data Analysis**

**Sample and Setting.** All research procedures will be performed in the TUKSoD Clinic at Kleinlife and at the Dental School. Participation in the research is expected to take 1 hour regardless of study group. Seniors meeting the inclusion criteria will constitute the sample for the purpose of this study.

#### **Sample Selection Procedures**

All assessments will be conducted after informed consent has been obtained in person. Patients deemed ineligible or who do not wish to participate in the research will be referred for clinical services as appropriate. The decision to participate or not to participate in the research will have no effect on the dental treatment that the patient will receive. A sample of 190 seniors will be recruited from the TUKSoD Clinic at Kleinlife and at the Dental School for the purpose of this study.

#### **Study Procedure**

This will be a multi-center parallel group study with randomization to one of three arms as described below. The objective of this study is to test the efficacy of an oral health education group based activity versus an individual based oral health education activity in terms of changes in oral health related quality of life

## ORAL HEALTH EDUCATION SENIORS

(OHRQoL), and self-efficacy among seniors at Kleinlife and at the Dental School. A description of the activities to be conducted in the intervention and control groups is described below:

Seniors who consent to participate in the study will be randomly allocated to one of the 3 following groups. Randomization will be determined according to a predetermined random sequence, and neither the patient nor the research staff will be aware of the randomization outcome until after the patient has agreed to participation.

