## ORAL HEALTH EDUCATION SENIORS

KleinLife is a vibrant community resource that provides social, educational and cultural programs, and vital health, wellness and social services to the multigenerational, ethnically diverse membership it serves. Individuals regularly come together to participate in enrichment offerings, receive vital services, enjoy each other's company, and connect to additional resources and support. KleinLife is an important destination for the region's Jewish population, both young and old. It serves as a lively home-away-from-home for seniors and a welcoming gathering place for Russian Jews. More than 7800 health care referrals to seniors and their families have been made through KleinLife.

TUKSoD and KleinLife's staff conducted a survey in December 2015 to develop a baseline needs assessment that would inform the development and implementation of a tailored oral health care model in this community. Two hundred oral health surveys were completed and from this initial survey, we learned that there were variations in knowledge, attitudes and practices related to oral hygiene among seniors and lack of understanding of key fundamental concepts in oral health education and oral health related quality of life.

Recent studies on this area have mainly focused on the effects of oral health educational interventions for caregivers at improving dental health among seniors but very few interventions report on the oral health-related knowledge and other important behavioral outcomes of seniors themselves. MacEntee et al in 2007 reported no significant changes to oral health of seniors with a pyramid-based educational intervention, however, in 2012, De Visschere et al reported a small, but statistically significant improvement in denture plaque following a 6-month supervised educational intervention.

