### **7) Study Design**

#### **a) Recruitment Methods**

Approximately 190 subjects, older than 55 years old will be recruited for the purpose of the study. There are no restrictions in terms of relative numbers of females and males. Potential subjects will be obtained in person through the ongoing flow of patients at TUKSoD Clinic at Kleinlife and at the Dental School. The research staff will also be available during regular operating hours to inform and recruit patients at the lobby at Kleinlife and at the Dental School. The consent form (See Appendix A) to participate in the study will be provided to the senior and if they decide to participate they will be entered into a raffle to receive a \$350-dollar visa gift card, if they complete the baseline and follow up assessments. The information from the consent forms will only be used for the purpose of the raffle. This is required for compliance with Pennsylvania state laws. Information about the study will also be posted in a flyer (See Appendix B) in designated areas at Kleinlife and at the Dental School.

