### **Control Group: (60 seniors).**

Seniors who are randomly assigned to the control group will continue receiving regular dental care under the standard clinic operation. Subjects in this group will complete intake forms to assess main behavioral outcomes, at baseline and after 12 months. No other activities will be conducted in this group.

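### With individual randomisation, no household limit and no record of exposure to the study's teaching, the education contrasts may be diluted and nobody could tell

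*Combined protocol and SAP*

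**What the plan says.** **Allocation.** Section 7 d), Study Procedure, makes the individual senior the unit of randomisation: "Seniors who consent to participate in the study will be randomly allocated to one of the 3 following groups". On method it adds only that "Randomization will be determined according to a predetermined random sequence". No rule for households, sites or blocks is described.

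**Setting.** Section 7 a) takes participants from two places: "Potential subjects will be obtained in person through the ongoing flow of patients at TUKSoD Clinic at Kleinlife and at the Dental School". Staff will also "inform and recruit patients at the lobby at Kleinlife and at the Dental School". Section 5 says of Kleinlife that "Individuals regularly come together to participate in enrichment offerings, receive vital services", and "It serves as a lively home-away-from-home for seniors". Nothing comparable is said of the Dental School.

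**Eligibility.** The criteria in section 7 b) cover age, patient status, English and consent. They are silent on spouses and housemates.

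**Arms.** Controls have usual care and questionnaires at baseline and 12 months; the control-group paragraph ends "No other activities will be conducted in this group". Intervention 1 invites its assigned seniors to two group sessions. Intervention 2 combines individual motivational interviewing, tailored to the senior's own records, with preventive care.

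**Measurement and analysis.** The Appendix C instruments cover demographics, self-efficacy, OHIP-14 and knowledge. None asks about living arrangements, enrolled relatives or teaching received through another participant. The one fidelity check, audio recording, concerns the hygienist's delivery to 10 calibration patients outside the trial. Data Analysis plans an intention-to-treat analysis with no examination of contamination.

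**The concern.** Part of what is being tested is information, and information can pass between people who live together or meet often. A control who learns the curriculum from an educated spouse or friend is still analysed as a control. If that control benefits, the education-versus-control difference moves toward zero. Because no form records such exposure, a null result could mean that the education does not work or that some controls received part of it. The data would not separate the two, and exposure during follow-up is hard to reconstruct afterwards.

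A second consequence concerns the comparison of the two education arms. The second null hypothesis in section 4 is that these arms are not equivalent. Sharing between them would make them look more alike and so favour rejecting that null. There the error would be a false claim of equivalence, not just a loss of power.

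**Working it through.** **Inputs from the documents.** The arm headings give 60 controls, 60 in Intervention 1 and 70 in Intervention 2, of whom 10 are calibration patients only. The sum 60 + 60 + 70 = 190 matches the stated sample; 190 − 10 = 180 leaves 60 per arm for analysis. Data Analysis sets significance at 0.05; I assume this is two-sided.

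**Not in the documents.** There is no target effect, SD, power, dropout rate, share of couples or rate of sharing. The plan therefore has no power figure to reproduce, and steps 2 to 4 are illustrations.

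**Step 1: how often a couple is split.** Assume independent allocation with probability 1/3 per arm.
- One partner in control and the other in an education arm: 2 × (1/3) × (2/3) = 4/9 = 44%.
- For a control whose partner also enrols, the partner is in an education arm with probability 2/3.

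**Step 2: a reference effect.** For one pairwise contrast with 60 per arm, the difference detectable with 80% power is (1.960 + 0.842) × √(2/60) = 0.51 SD by the normal approximation. An exact two-sample t-test gives 0.52 SD.

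**Step 3: power after dilution.** Let c be the share of the contrast that is lost. The observed effect is d(1 − c), power is Φ(d(1 − c)√(60/2) − 1.960) with d = 0.5115, and the number needed to restore 80% is 60/(1 − c)², rounded up.

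| c | Effect left (SD) | Power, 60 per arm | n per arm for 80% |
|---|---|---|---|
| 0% | 0.51 | 80% | 60 |
| 10% | 0.46 | 71% | 75 |
| 20% | 0.41 | 61% | 94 |
| 30% | 0.36 | 50% | 123 |

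The t-test version gives the same rounded powers.

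**Step 4: what couples alone could contribute.** Let h be the share of controls with an enrolled partner and t the fraction of the benefit passed on. Then c = h × (2/3) × t. Both h and t are assumed.

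| h | c and power, full transfer (t = 1) | c and power, half transfer (t = 0.5) |
|---|---|---|
| 10% | 7%, 74% | 3%, 77% |
| 20% | 13%, 68% | 7%, 74% |
| 30% | 20%, 61% | 10%, 71% |

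The loss is small if few couples enrol or little is passed on. It becomes serious only toward the top of the range.

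**The case against.** Several stronger readings are tempting, and the documents do not support them.

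- **That the whole trial sits in one social community.** It does not. Recruitment also covers the Dental School, and the design is stated as "This will be a multi-center parallel group study with randomization to one of three arms as described below". The evidence of regular social contact concerns Kleinlife only, and the split of participants by site is not given. The household route, however, is open at both sites.
- **That the education simply passes from person to person.** Much of Intervention 2 cannot: a partner does not hand on a cleaning, a varnish application or an interview tailored to someone else's records. Data Analysis names OHIP-14 and self-efficacy as the primary outcomes, and second-hand facts would more plausibly move knowledge. Knowledge does appear in the primary objective in section 4, and its 15 factual statements are easily repeated. The full-transfer figures are therefore upper bounds.
- **That controls are free to attend sessions.** The arm descriptions already tie sessions to the assigned group, and no take-home written materials are described. The remaining route is conversation. The consent form is not available here, so any request in it not to share cannot be checked; such a request would still leave exposure unmeasured.
- **That the power losses are findings about this trial.** They start from whatever effect gives 80% power and shrink it, so similar percentages would arise at any sample size. They also use a two-group comparison, whereas the main analysis is a repeated-measures mixed model. They show sensitivity, not the size of a known loss.
- **That correlated partners undermine the analysis.** Within any one pairwise contrast a couple shares an arm with probability 2 × (1/9) = 2/9 and is split with probability 2 × (1/9) = 2/9. Positive correlation raises the variance in the first case and lowers it equally in the second, so the expected net effect is about nil.

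Individual randomisation is also a legitimate choice, and dilution works against a positive education-versus-control result. What stands is narrower: a foreseeable route for sharing is neither limited nor measured.

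**Conclusion.** The point holds as a gap in design and data collection that is cheap to close. It is not evidence that the result will be biased by a known amount. Members of one household may enter different arms, at 44% control-versus-education for a couple if allocation is independent and 1:1:1, and no form would reveal that teaching had been shared. Education-versus-control contrasts may be diluted, mainly for knowledge and the group curriculum, and the two education arms may look falsely alike.

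The size is unknown. For an effect of about 0.52 SD with 60 per arm, power would be 71% to 50% if 10% to 30% of the contrast were lost. Through couples alone it would be 77% to 61% over the assumed range in step 4. A reader might infer that the effect is diluted, or that individual randomisation should be abandoned; the documents establish neither.

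**What to change.** 1. **Exclusion criteria, section 7 b).** Add that only one member of a household may be enrolled, and that a second member who asks to join is referred for usual services.
2. **Every follow-up form, all arms.** Add one item, placed after the outcome instruments, for example: *Since joining the study, have you attended any of this study's oral health education sessions other than your own, or has another participant told you what was taught at one? Please do not count ordinary advice given during your regular dental visits.* The last sentence matters because controls continue regular care and will hear chairside advice. Asking about the whole period since joining suits arms that complete different numbers of follow-up forms.
3. **Data Analysis.** State that reported exposure will be tabulated by arm and by site (Kleinlife, Dental School) as a descriptive aid to reading the intention-to-treat result. It arises after randomisation and should not redefine the groups.

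**Cost.** One eligibility line, one questionnaire item and one table. A few second household members cannot enrol. The recruitable pool is smaller than the 6500 seniors cited for Kleinlife, because eligibility requires English and being, or intending to become, a clinic patient, but the loss should still be small. The household rule does not prevent sharing between friends; the new item only measures it. The item should be in place before follow-up begins.

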### **Control Group: (60 seniors).**

Seniors who are randomly assigned to the control group will continue receiving regular dental care under the standard clinic operation. Subjects in this group will complete intake forms to assess main behavioral outcomes, at baseline and after 12 months. No other activities will be conducted in this group.

### **Intervention Group 1: (60 seniors).**

Seniors who are randomly assigned to the intervention group 1 will continue receiving regular dental care under the standard clinic operation and will be invited to participate in 2 group based education activities over a 12 month period. The sessions will last for 1 hour each time and follow the guidelines established by the Oral Health America Curriculum. Baseline intake forms to assess changes in main behavioral outcomes will be administered before the first education session, after 6 months and after 12 months.

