### **Data Analysis:**

Initial analyses will be conducted to determine normality of distributions of the continuous variables, and any necessary transformations will be conducted. Primary outcomes will be the OHIP 14 and the self-efficacy scores. All eligible patients will be randomly assigned to 1 of the 3 groups described above. Although randomization should provide relatively comparable groups, demographic variables that differ between groups and are correlated with the primary outcomes will be used as covariates. Preliminary analysis will include measures of central tendency and dispersion, as well as an examination of the bivariate relationships among the primary and secondary outcome variables, potential moderators, and demographic characteristics.

Differences between the groups on baseline demographic, and psychological measures will be examined using  $\chi^2$  (Pearson) or Student's *t*-tests, as appropriate. Moreover, differences on the variables listed above among completers and drop-outs will also be explored. Intention to treat (ITT) analyses will then be conducted.

OHIP 14 and self-efficacy scores will be the primary outcomes. Initially, we will assess the differences between the interventions and control using 2-sample *t*-tests. The main analysis will be based on linear mixed-effects models for repeated measures (using the OHIP 14 and self-efficacy scores as continuous outcome variables) to assess differences between intervention and control groups. Similar analyses will be conducted for secondary outcome measures. Statistical significance will be set at  $p < .05$ .

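### Only Group 1 is taught in shared sessions, but the analysis plan names no session-group effect; if outcomes correlate within session groups, standard errors for contrasts involving Group 1 will be too small

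*Combined protocol and SAP*

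**What the plan says.** All references are to section 7 of the combined protocol and SAP unless stated.

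- **Randomisation (Study Procedure).** The unit is the individual: "Seniors who consent to participate in the study will be randomly allocated to one of the 3 following groups".
- **Delivery.** Group 1 seniors "will be invited to participate in 2 group based education activities over a 12 month period", each lasting an hour. Group 2 receives individual education from a public health hygienist. Control receives usual dental care only.
- **Analysis (Data Analysis).** First, "we will assess the differences between the interventions and control using 2-sample" t-tests. Then: "The main analysis will be based on linear mixed-effects models for repeated measures", with OHIP-14 and self-efficacy as continuous outcomes. "Statistical significance will be set at" p < .05, and "Intention to treat (ITT) analyses will then be conducted".

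The only dependence named is between repeated measurements. The random effects of the mixed model are not listed. The documents do not give the number or size of session groups, whether the same seniors meet on both occasions, an ICC, or a data field for session group.

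**The concern.** This is a partially nested design: individual randomisation, with one arm of three delivered to people together. Seniors who share a session share its content, occasion and discussion. Section 5 describes KleinLife as a place where members meet regularly, so some peer influence is plausible. Any resulting correlation adds a between-session component to the variance of the Group 1 mean. A t-test on individuals leaves that component out. So does a mixed model whose only random effect is for the person.

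Two contrasts are at stake: group versus control, and group versus individual. For both, intervals would be too narrow and p-values too small. The second hypothesis in section 4 is framed as equivalence, and there too an interval that is too narrow could make a claim look better supported than it is. The remedy also depends on timing: if nobody records who was assigned to which session group, the analysis may be impossible to repair afterwards.

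**Working it through.** **Inputs from the documents.** Control 60, Group 1 60, Group 2 70, of whom 10 are calibration patients outside the trial. The sizes add up (60 + 60 + 70 = 190) and leave 180 for comparison. The significance level is 0.05, with sidedness not stated. The plan gives no effect size, SD or power, so it has no power figure to reproduce.

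**Assumptions.** A two-sided test; one follow-up comparison of 60 v 60; equal total variance in both arms; m seniors per session group; ICC ρ from 0 to 0.10; full attendance at first. For group versus individual, any effect of the hygienist on Group 2 is left aside; the text refers to a single hygienist, so that effect could not be separated from the arm.

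**Formula.** Sharing inflates the variance of the Group 1 mean by DE = 1 + (m − 1)ρ. The comparator is not inflated, so

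- R = true SE / unclustered SE = √[(DE + 1)/2]
- actual error rate = 2 × [1 − Φ(1.96/R)]

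**Example, m = 10, ρ = 0.05.** DE = 1 + 9 × 0.05 = 1.45. R = √1.225 = 1.107. 1.96/1.107 = 1.771, which gives 7.7%.

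| m (groups) | ρ | DE | R | Actual error rate |
|---|---|---|---|---|
| any | 0 | 1.00 | 1.000 | 5.0% |
| 5 (12) | 0.01 | 1.04 | 1.010 | 5.2% |
| 5 (12) | 0.05 | 1.20 | 1.049 | 6.2% |
| 5 (12) | 0.10 | 1.40 | 1.095 | 7.4% |
| 10 (6) | 0.01 | 1.09 | 1.022 | 5.5% |
| 10 (6) | 0.05 | 1.45 | 1.107 | 7.7% |
| 10 (6) | 0.10 | 1.90 | 1.204 | 10.4% |
| 20 (3) | 0.01 | 1.19 | 1.046 | 6.1% |
| 20 (3) | 0.05 | 1.95 | 1.214 | 10.7% |
| 20 (3) | 0.10 | 2.90 | 1.396 | 16.0% |

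**Simulation check.** With 20,000 trials per cell, the unclustered t-test rejected 7.7% of the time at m = 10, ρ = 0.05, and 10.9% at m = 20, ρ = 0.05. At ρ = 0 it rejected 4.5% to 5.1%. Adjusting for baseline, with an assumed baseline to follow-up correlation of 0.5, raised the first figure to 8.4%.

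**Partial attendance.** If a fraction q attends in groups of m, R² = 1 + q(m − 1)ρ/2. At m = 10, ρ = 0.05:

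- q = 0.8: R² = 1.18, error rate 7.1%
- q = 0.5: R² = 1.1125, error rate 6.3%

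**Information lost.** At m = 10, ρ = 0.05, the 60 seniors carry the information of 60/1.45 ≈ 41. Power for an assumed 0.5 SD difference falls from 78% to 70%.

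**How well a session-level analysis holds 5%.** Using session-group means with Satterthwaite degrees of freedom, over ρ = 0 to 0.10, the simulated error rate was 4.8% to 5.6% with 5 to 12 groups, 5.0% to 5.8% with 4, 5.6% to 7.0% with 3, and 6.6% to 10.8% with 2. With one group the session effect cannot be estimated.

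**Where the random effect must sit.** Group 1 baseline forms are completed before the first session, so a session effect arises only afterwards. Suppose baseline is modelled as a response and the effect of interest is arm by time. A time-constant session intercept u enters both the baseline and the later score, so it cancels from their difference: (u + later) − (u + baseline). The real post-baseline session effect does not cancel. It stays in the change and is still missing from the standard error.

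**The case against.** A reader might infer that the standard errors are wrong and that the 5% level is lost. The documents do not support that. Both depend on a positive ICC and on session size, and neither is given. At ICC 0 nothing changes, and at 5 per group with ICC 0.01 the error rate is 5.2%. That part of the objection stands, and the point is therefore conditional.

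A reader might also infer that the mixed model has been specified to ignore sessions. That is inference from silence, since no random effects are listed. For the t-tests it is not inference: they assume independence.

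Other objections hold in part:

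- Exposure is slight: two one-hour sessions, by invitation, analysed by intention to treat. Partial attendance shrinks the inflation but does not remove it.
- The documents do not say who leads the group sessions or how interactive they are. If one educator led them all, that person's effect would belong to the arm and would not be within-session correlation.
- Not every main comparison is affected. Individual versus control involves no shared sessions.
- The error rates concern the null of no difference and do not carry over as figures to the equivalence hypothesis.

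The missing size and ICC are not a reason to drop the point. The unnamed model term and the absent data field can be seen in the text, and the trial can estimate the ICC only if session group is recorded.

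**Conclusion.** The concern holds as a conditional one. The plan teaches one arm in shared sessions and names no analysis that allows for it. If outcomes correlate within session groups, contrasts involving Group 1 will look more precise than they are. Over the assumed range of 10 to 20 per group and ICC 0.01 to 0.10, the unclustered standard error is 2% to 28% too small (1 − 1/R), and the actual error rate is 5.5% to 16.0%. With small groups and a very low ICC the effect is negligible. The direction is certain for any positive ICC; the size rests on assumptions the documents can neither confirm nor exclude. The change should be made before Group 1 sessions are organised, because it needs data collected prospectively.

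**What to change.** **In Intervention Group 1:** state the planned number and size of session groups and whether membership is the same for both sessions. Assign every Group 1 senior to a session group and record its identifier, whether or not the senior attends, so that the analysis stays by intention to treat. Plan several groups; one to three are too few.

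**In Data Analysis:** for contrasts involving Group 1, replace the unclustered t-tests with a partially nested mixed model.

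- Keep the within-person correlation, and add a session-group random effect in Group 1 only, with control and Group 2 seniors as singletons.
- Let that effect act on post-baseline outcomes. Either use the baseline score as a covariate or, if baseline is a response, fit a session-by-post-baseline effect. A time-constant session intercept is not enough.
- Use Satterthwaite or Kenward-Roger degrees of freedom, and report the ICC.

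**Cost.** One extra data field and a short analysis text. Assignment to session groups must be organised, which takes some effort when recruitment follows ongoing patient flow. Intervals for Group 1 contrasts widen to reflect a true standard error about 2% to 40% larger at 10 to 20 per group over ICC 0.01 to 0.10, and some degrees of freedom are lost. If the ICC proves close to zero, little is given up beyond those degrees of freedom.

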### **Intervention Group 2: (70 seniors (10 of these are calibration patients exclusively)).**

Seniors who are randomly assigned to the intervention group 2 will continue receiving regular dental care under the standard clinic operation and will also be invited to participate in an individual-based education activity over a 12 month period. The clinic visits will last for 1 hour each time and follow the guidelines established by TUKSoD to provide oral hygiene instruction using a Motivational Interviewing approach. Tailored education will be based on review of health related information to be extracted from medical (systemic diseases), dental chart (oral hygiene behaviors) and patient interview at time of initial examination. Seniors in this group will also receive basic preventative care (dental cleanings, fluoride varnish application (high caries risk individuals only) or referral to a supervised brushing program with high concentration fluoride under the care of the dentist at Kleinlife if needed. All individual based preventative activities will be provided by a Public Health Hygienist, and 3 dental visits will be conducted for subjects in this group during the course of a 18 month period. Baseline intake forms to assess changes in main behavioral outcomes will be administered before the first home based education session, at each follow up visit and after 18 months.

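### The plan does not require baseline questionnaires to be completed before allocation is disclosed, and it anchors them differently by arm

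*Combined protocol and SAP*

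**What the plan says.** All references are to section 7(d) of the combined protocol and SAP unless stated otherwise.

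- **Order of events (Study Procedure).** "Seniors who consent to participate in the study will be randomly allocated to one of the 3 following groups", and "neither the patient nor the research staff will be aware of the randomization outcome until after the patient has agreed to participation". Concealment is promised up to agreement and no further.
- **Earliest time of any assessment (Sample Selection Procedures).** "All assessments will be conducted after informed consent has been obtained in person". Nothing is said about allocation.
- **Control Group.** "Subjects in this group will complete intake forms to assess main behavioral outcomes, at baseline and after 12 months". No event defines baseline.
- **Intervention Group 1.** Participants "will be invited to participate in 2 group based education activities over a 12 month period". The baseline forms "will be administered before the first education session, after 6 months and after 12 months".
- **Intervention Group 2.** The baseline forms "will be administered before the first home based education session, at each follow up visit and after 18 months". The same paragraph otherwise describes clinic visits, so even the event that serves as the anchor is unclear.
- **Data Management.** Questionnaires are given in person. Imputation depends on how much is missing, and no method is named.
- **Data Analysis.** The primary outcomes are OHIP-14 and self-efficacy. The main analysis is a linear mixed-effects model for repeated measures, preceded by two-sample t-tests. Only demographic covariates are mentioned. Intention to treat is stated but the set is not defined.

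**The concern.** The primary objective (section 4) is framed in terms of changes, so the baseline score carries as much weight as the follow-up score. Both primary outcomes are participants' own ratings: OHIP-14 rates how often oral problems intrude on daily life, and the self-efficacy scale rates confidence in brushing. Someone who knows that counselling or a class is coming may answer these differently from someone who knows that nothing extra is coming. If baseline is taken after disclosure, such a difference enters the treatment comparison.

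The second route is missing data. Education sessions are by invitation. If the forms are handed out at the first session, a participant who never comes may have no baseline. The control arm has no session to miss, so this kind of loss could be confined to the intervention arms, and people who skip sessions are unlikely to be a random subset.

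**Working it through.** **The plan's own figure.** The arms sum to 60 + 60 + 70 = 190, as stated. Removing the 10 calibration patients leaves 180, or 60 per arm. The plan gives no SD, effect size, attendance rate or correlation, so the size of the problem can only be illustrated.

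**Reading the sections together.** Study Procedure gives consent, then allocation, with disclosure possible once the patient has agreed. No baseline step is named between them. Baseline first appears in the three arm descriptions, as something done by seniors already assigned to that arm. In the intervention arms the latest permitted moment is the first session. By then participants must have been invited to it, and section 7(f) gives the HIPAA authorization form only to those assigned to Intervention Group 2. A baseline taken just before that session complies with the plan and is unblinded.

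**Illustration 1: non-attenders without a baseline are dropped.** Assumptions: a share w of one intervention arm is lost, and the lost participants differ from the rest of the arm by d = 0.5 SD.

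- Bias of the arm mean = w × d. SE = √(1/60 + 1/(60(1 − w))). Two-sided rejection rate with no true effect = Φ(t − 1.96) + Φ(−t − 1.96), where t = bias/SE.
- w = 0.10 (6 of 60): bias 0.05 SD; SE = √(1/60 + 1/54) = 0.188; t = 0.27; rejection rate 5.8%.
- w = 0.20 (12 of 60): bias 0.10 SD; SE = √(1/60 + 1/48) = 0.194; t = 0.52; rejection rate 8.1%.
- For scale, the difference detectable with 80% power at 60 per arm is (1.960 + 0.842) × √(2/60) = 0.511 SD by the normal approximation. The two biases are about 10% and 20% of it.

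**Illustration 2: knowledge of the arm shifts baseline.** Assumptions: one arm's baseline mean moves by b SD, follow-up is unaffected, there is no true effect, there are 60 per arm, and the baseline to follow-up correlation is ρ.

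- Change score: bias b; SE = √(2(1 − ρ)) × √(2/60).
- Baseline-adjusted: bias ρb; SE = √(1 − ρ²) × √(2/60).

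| ρ | b (SD) | Change score, rejection rate | Baseline-adjusted, rejection rate |
|---|---|---|---|
| 0.5 | 0.1 | 8.5% | 6.2% |
| 0.5 | 0.2 | 19.5% | 9.7% |
| 0.5 | 0.3 | 37.6% | 15.8% |
| 0.3 | 0.2 | 15.2% | 6.4% |
| 0.7 | 0.2 | 29.3% | 18.9% |

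For ρ = 0.5 and b = 0.2, the change-score SE is 1 × 0.183 and t = 1.10; the adjusted SE is 0.866 × 0.183 = 0.158 and t = 0.10/0.158 = 0.63. With baseline completed before disclosure, knowledge of the arm cannot move it. Then b = 0 and this source of error disappears.

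**The case against.** The strongest reply is that the plan never says baseline follows disclosure. Requiring forms before the first session sets only a latest time, and the rule that assessments follow consent is compatible with completing them at the consent visit before the allocation is opened. All three arms call them intake forms, which fits completion at enrolment. This stands: a reader might infer that baseline is taken unblinded, but the documents only permit it.

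The missing-baseline route is likewise an inference. No section says that the forms are handed out at the session. Section 7(a) ties raffle entry to completing the assessments without mentioning sessions, although section 11 speaks of completing participation as a whole. Nor does the plan guarantee a baseline for every control.

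A reader might also conclude that missing baselines defeat the intention-to-treat analysis. That goes too far. A mixed model with baseline as one of the repeated responses can keep a participant who has only later scores, imputation is foreseen, and a t-test on follow-up scores alone would not need baseline. But the plan specifies neither the model's use of baseline nor the analysis set, so these are possibilities and not safeguards. Keeping such participants also does nothing about a shifted baseline.

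Finally, the knowledge questionnaire is a factual test. Expecting to be taught is not an obvious reason to answer it differently, so the argument about self-report is confined to OHIP-14 and self-efficacy.

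**Conclusion.** The point holds as a gap in the procedure. The plan does not require baseline before disclosure, and its arm-specific wording suggests that baseline follows allocation. It therefore allows an unblinded baseline, timed differently by arm, for both primary outcomes. It does not establish that this will happen, that non-attenders will lack a baseline, or that intention to treat fails.

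The size and direction are unknown. The 5.8% to 8.1% range rests on assumed non-attendance of 10% to 20%, an assumed 0.5 SD difference, and complete exclusion of those without a baseline. The larger figures for a shifted baseline rest on assumed shifts and correlations. A reader might add the two effects together, but the documents give a direction for neither, and they could offset each other.

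The plan should still be changed. A baseline distorted by knowledge of the arm cannot be reliably corrected in the analysis, whereas preventing it takes little more than a sentence.

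**What to change.** In section 7(d), Study Procedure, and in the three arm descriptions, state that:

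1. participants in all three arms complete the baseline forms after consent and before allocation is disclosed to them or to the research staff;
2. this applies regardless of later session attendance;
3. each arm's already scheduled follow-up times are counted from the date of the baseline forms.

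Replace the references to the first education session as the baseline anchor, and reconcile the home-based description in Intervention Group 2 with the clinic visits described there. It would help if Data Analysis also said how the baseline score enters the model and who belongs to the intention-to-treat set.

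The cost is small: form-filling time moves to the consent visit. Sample size and the number of assessments do not change. The differing follow-up schedules (12 versus 18 months, and a month-6 assessment specified in one arm only) are a separate matter to reconcile. This change neither settles them nor adds an assessment to any arm.
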